The temporomandibular joint (TMJ) is the only diarthrodial articulation of the human joints. It is known as ginglymo-arthrodial joint and is formed by the bony articulations of the mandibular condyle with the glenoid fossa of the temporal bone. Interposed between the condyle and the fossa is a piece of dense avascular fibrous connective tissue namely the TMJ disc. The disc divides the joint into superior and inferior compartments, which normally do not communicate with each other. The condyle and disc are in a normal anatomic relationship if the posterior band of the disc is located above the condylar head when the mandibular condyle is centrally positioned in the fossa.⁽¹⁾

The prevalence of temporomandibular disorders (TMD) is thought to be greater than 5% of the population.⁽²⁾ Lipton and colleagues⁽³⁾ showed that about 6% to 12% of the population experience clinical symptoms of TMD. Patients with TMD symptoms present over a broad age range; however, there is a peak occurrence between 20 and 40 years of age.⁽⁴⁾ TMD symptoms are more prevalent in women than men. Women tend to develop TMD during their premenopausal years. The reasons behind the sexual disequilibrium in TMD prevalence are not entirely clear, but some have suggested a hormonal influence.⁽⁵⁻⁷⁾

Temporomandibular disorders (TMD) are a broad group of clinical problems involving the masticatory musculature, the temporomandibular joint, surrounding bony and soft tissue components, and combinations of these problems. Temporomandibular disorder (TMD) can result from any defect of one or both. Any problem that prevents this composite system of muscles, bones and joints from working in harmony may result in this disorder. Symptoms may be unilateral or bilateral and involve the face, head or jaw. The American Academy of Orofacial Pain (AAOP) classification divides TMD broadly into muscle related TMD (myogenous), and joint-related TMD (arthrogenous). The two types can be present at the same time, making diagnosis and treatment more challenging.⁽⁸⁾

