IV	Chronic pain Headaches Restricted motion with crepitus	Anterior disk displacement that does not recapture on opening Marked disk deformity Degenerative osseous changes	Disk perforation, displacement, and adhesions Degenerative changes in condyle and/or fossa
V	Variable pain Joint crepitus	Anterior disk displacement that does not recapture on opening Marked disk deformity Degenerative osseous changes	Disk perforation, displacement, and adhesions Degenerative changes in condyle and/or fossa

Diagnosing TMD requires a focused history and physical examination. Pain and limited range of motion are accepted symptoms of TMJ dysfunction. In general, patients with true intra-articular pathology have pain that is localized to the involved TMJ, which is increased with mandibular movement or masticatory function. Failure to reproduce pain localized directly to the involved TMJ, stimulated with masticatory load and/or movement, is a warning that the main cause of pain may not be intra-articular, even with magnetic resonance imaging (MRI) confirmed disc displacement. ⁽¹²⁾ Radiographic studies can also be used as supplemental diagnostic tools. Periapical radiographs can be used to rule out dental pathologies as a cause of referred pain. Cone beam computed tomography scans and panoramic radiographs will provide detailed imaging of the joint's bony structures but not the articular disk. MRI is the modality of choice for examining the disk position and morphology (gold standard). MRI may also show degenerative bony changes. MRI findings should not alone dictate treatment strategies. One must combine patients' clinical presentation, signs, and symptoms along with TMJ imaging when developing a treatment plan. The surgeon must treat the patient, not the MRI. Studies have revealed MRIs in asymptomatic subjects demonstrate disc displacement in the range of 32-38%.⁽¹²⁾ On MRI, joint effusions are radiographic signs of inflammation and an important finding in true intra-articular pathology.⁽¹³⁾ Inflammation indicates a transition from adaptive to pathologic changes within the joint. The MRI diagnosis of

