According to Murakami on the rationale of arthroscopic surgery of the TMJ, he stated that, although various arthroscopic disc repositioning and suturing techniques were reported, the success rate was comparable to arthroscopic lysis and lavage, and the documentation by postoperative imaging was insufficient.⁽²⁴⁾

According to Israel: Numerous intra-articular operative arthroscopic techniques have been reported in the literature since the advent of temporomandibular joint (TMJ) arthroscopy. However, Ideal randomized controlled trials regarding outcomes are lacking nor are their strong evidence supporting one operative technique over another.⁽¹⁵⁾

Nowadays, minimally invasive procedures have eliminated the use of many of the more complex surgical procedures. Despite such advancements, however, clinicians are still encountering some difficulty in successfully treating many of these patients and finding the answers to these problems will

depend on future developments.

A review of the literature reveals that there is lack of randomized clinical trials to compare between the three levels of TMJ arthroscopy in the management of TMJ internal derangement.

The null hypothesis states that there will be no significant difference between the three levels of TMJ arthroscopy. Consequently, by doing the necessary studies and comparing the results, we can accept or reject this theory to finally develop guidelines and standardized patient selection criteria that can be followed by all researchers.

AIM OF THE STUDY

To compare between the three levels of TMJ arthroscopy in the management of TMJ internal derangement in the following points:

Primary aims are to assess:

1. Pain score using the visual analog score (VAS).⁽²⁵⁾
2. Presence or absence of clicking.
3. Mouth opening measuring the maximal interincisal opening in MIS.
4. Lateral excursion movement.
5. Protrusive movement.

[figure not shown]
Secondary aims are to assess:

1. Operative time.
2. Post operative MRI (disc position).

CONSORT

TRANSPARENT REPORTING of TRIALS

Study design

This study will be a randomized controlled clinical trial, with 1:1:1 ratio and will be reported according to CONSORT guidelines ⁽²⁶⁾

PICO Question

Do patients with TMJ internal derangement treated with arthroscopy level I compared to arthroscopy level II or arthroscopy level III show better maximal interincisal opening and less pain?

Settings and Location:

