Participants will be selected from the Maxillofacial and Plastic Surgery Department, Faculty of Dentistry, Alexandria University, Egypt.

Sample size calculation

The size was estimated based on 5% alpha error and 80% study power. The mean (SD) improvement in Maximum Interincisal Opening (MIO) after 6 months compared to the preoperative measurements was 6.09 (7.05) mm for Level I arthroscopy, (10) 6.7 (5.25) mm for Level II arthroscopy, ⁽²⁷⁾ and 18.5 (2.1) mm for Level III arthroscopy. ⁽²⁸⁾ Based on difference between independent means using F test and pooled SD = 4.8 mm, the minimum sample size was calculated to be 9 joints per group, increased to 10 joints to make up for lost to follow up cases. Total sample = number per group x number of groups = 10 x 3 = 30 joints. Sample size was based on Rosner's method ⁽²⁹⁾ calculated by G*Power 3.1.9.7. ⁽³⁰⁾

Randomization

Participants will be randomly assigned using online program (www.random.org) in order to allocate participants to the group.

Allocation Concealment

Sequentially numbered opaque sealed envelopes will be used to conceal allocation. One set of envelopes will be created to guarantee they were opaque, sealed and sequentially numbered.

Blinding

The patients will be blinded to the treatment group.

Intervention

Group I: 10 patients will be treated with level (I) arthroscopy (Lysis and lavage).

Group II: 10 patients will be treated with level (II) arthroscopy (operative arthroscopy).

Group III: 10 patients will be treated with level (III) arthroscopy (operative arthroscopy + disc repositioning and fixation).

Eligibility Criteria

Inclusion criteria

The patients with TMJ internal derangement will be divided into 5 stages according to Wilkes Classification.⁽¹¹⁾ Only patients with stage III will be

included in this study.

Exclusion criteria

1. Medically unfit patients.
2. Patients with TMDs secondary to malocclusion.
3. Psychological instability.
4. Patients operated before for other TMJ problems.

Materials

In all procedures, 1.9 mm, 30-degree optical device, sleeves, sharp and blunt trocars, adhesion knives, an exploratory probe, a bipolar electrode (Karl Storz Endoscopy, Tuttlingen, Germany) and coblator.

A specific material for pin placement is A third custom-made cannula (2.7mmdiameter) with a distal parallel double window (10 _ 2 mm) for direct view control of pin fixation, a long 1.5-mm rotatory drill for perforating disc and condyle, and an impactor with hammer (fixation kit).

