2. Short hospital stay with early recovery and rapid return to work.

The risks to the participant and/or the community

1. The need for long-term follow-up postoperative.
2. The exposure to radiation in MRI which is needed for follow-up at 6 months.

Anonymity and Confidentiality

The anonymity and confidentiality of the participants will be preserved by not revealing their names and identity in the data collection, analysis and reporting of the study findings.

The identity of participants will be kept confidential or anonymous and the assurances extend beyond protecting their names to also include the avoidance of using self-identifying statements and information.

DATA MANAGEMENT & STATISTICAL ANALYSIS

Data will be collected and analyzed statistically using ANOVA test to compare between the three groups.

REFERENCES

2. Thapliyal GK. Peterson's Principles of Oral & Maxillofacial Surgery. *Med J Armed Forces India.* 2006;62(1):89-.

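### Wilkes stage is applied to the patient, no study joint is named, and the other joint's status is neither a listed baseline item nor part of the analysis

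*Combined protocol and SAP*

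**What the plan says.** Eligibility is written for people: "The patients with TMJ internal derangement will be divided into 5 stages according to Wilkes Classification", and only stage III patients are included. The Wilkes table in the Introduction defines the stages largely by findings in a joint (disc position and form, adhesions, condyle and fossa). Its clinical column for stage III includes locking and restricted motion.

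The Introduction also says of temporomandibular disorders: "Symptoms may be unilateral or bilateral and involve the face, head or jaw". The exclusion criteria touch other joint disease only through previous surgery. No section says how a patient whose two joints differ in stage is to be staged, or whether the other joint is excluded, treated, listed as a data item or adjusted for.

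The Abstract counts 30 patients, and Sample size calculation counts 30 joints. The primary aims include protrusive movement, VAS pain and "Mouth opening measuring the maximal interincisal opening in MIS". The whole analysis plan is one sentence: "Data will be collected and analyzed statistically using ANOVA test to compare between the three groups".

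**The concern.** MIO and protrusion are movements of the whole mandible, so each patient has one value. By the protocol's own table, a stage III joint restricts motion. If the study joint is treated and the opposite joint also locks, the second joint may limit the measured gain whichever level the first received. This remains true with one study joint per patient and the patient as the unit of analysis, so it is separate from the question of counting joints or patients.

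The factor can be known before allocation. Left out of the model, it sits in the error term, and with 10 per arm and no stratification stated it may be unevenly spread by chance. The trial also aims to produce standardized selection criteria, and a rule that does not say which joint is staged cannot be reproduced by others.

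**Working it through.** **Inputs from Sample size calculation.** "The size was estimated based on 5% alpha error and 80% study power". Planned 6-month MIO gains, mean (SD): "6.09 (7.05) mm for Level I arthroscopy", "6.7 (5.25) mm for Level II arthroscopy" and 18.5 (2.1) mm for Level III. Common SD 4.8 mm; 9 joints per group, raised to 10.

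**The plan's own figure.** The mean of the three means is 10.43. f = sqrt[(4.34² + 3.73² + 8.07²)/3]/4.8 = 5.71/4.8 = 1.19. The one-way F test then has 88.0% power at 4 per group and 99.97% at 9. The stated 9 is therefore not reproduced; it exceeds what these inputs need. That is a separate matter and does not bear on this point.

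**Assumptions not in the documents.** A share p = 30% (range 20-40%) of patients has a second restricting joint, which costs L = 3 to 9 mm of MIO gain, equally in every arm.

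**Chance imbalance.** With X and Y independent Binomial(10, p), the probability that two arms differ is:

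| p | by 2 or more patients | by 3 or more patients |
|---|---|---|
| 20% | 39% | 16% |
| 30% | 46% | 22% |
| 40% | 49% | 25% |

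A difference of 3 in 10 shifts a contrast by 0.3 × L: 0.9, 1.8 or 2.7 mm for L = 3, 6 or 9. The planned Level I versus II difference is 6.7 − 6.09 = 0.61 mm. The standard error of that contrast is sqrt[(7.05² + 5.25²)/10] = 2.8 mm.

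**How large a loss fits the planned SDs.** The factor alone creates an SD of L × sqrt(0.3 × 0.7) = 0.458 × L, which is 2.75 mm at L = 6 and 4.1 mm at L = 9. Both exceed the planned Level III SD of 2.1 mm. If that SD already covers such a population, L cannot exceed 2.1/0.458 = 4.6 mm.

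**Precision gained by adjusting, Level III minus II.** The average planned variance is (49.70 + 27.56 + 4.41)/3 = 27.22. The factor contributes 0.21 × L². Estimating one more coefficient multiplies the half-width by about sqrt(1 + 1/27) × (2.056/2.052) = 1.02, where 27 is the residual degrees of freedom without the covariate and the t values are for 26 and 27.

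| Case | L (mm) | Ratio of half-widths, adjusted to unadjusted | Narrower by |
|---|---|---|---|
| SDs already include it | 3 | 1.02 × sqrt[(27.22 − 1.89)/27.22] = 0.98 | about 2% |
| SDs already include it | 4.5 | 1.02 × sqrt[(27.22 − 4.25)/27.22] = 0.94 | about 6% |
| Loss adds to SDs | 3 | 1.02 × sqrt[27.22/(27.22 + 1.89)] = 0.99 | about 1% |
| Loss adds to SDs | 6 | 1.02 × sqrt[27.22/(27.22 + 7.56)] = 0.90 | about 10% |
| Loss adds to SDs | 9 | 1.02 × sqrt[27.22/(27.22 + 17.01)] = 0.80 | about 20% |
| No effect | 0 | 1.02 | about 2% wider |

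Simulation with the unequal planned SDs agrees. In the additive case the mean half-widths without and with the covariate are 4.86 and 4.80 mm (L = 3), 5.37 and 4.85 mm (L = 6), and 6.07 and 4.85 mm (L = 9).

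**Effect on conclusions.** The planned Level III minus II difference is 18.5 − 6.7 = 11.8 mm. It was detected without the covariate in at least 98% of simulated trials, even at L = 9. Level I versus II has about 5-6% power at 9 per group in any case.

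**A different shape of loss.** If affected patients kept only a fraction of the planned gain, the contrast itself would shrink. With a quarter affected and half the gain kept, 11.8 becomes 11.8 × 0.875 = 10.3 mm, and F-test power at 9 per group is 98.5%. With half affected and no gain kept, it becomes 5.9 mm and power is 35%. The documents give no basis for choosing among these.

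**The case against.** The strongest reply is that the untreated other joint is an inference. No section says that one joint is operated on and the other left alone. If bilateral cases have both joints treated, no untreated joint remains and the issue becomes one of clustering, with 30 joints coming from as few as 15 patients. This stands, and it is why the fix starts by asking the protocol to say which applies.

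Several other objections stand in part:

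- Staging a patient is not simply an error, because the clinical column of the Wilkes table includes patient-level findings such as headaches. A reader might infer that someone with a stage IV or V opposite joint can certainly enter. The text leaves that unclear.
- Pre-surgical evaluation requires full history, examination and MRI without limiting them to one side, so the information is probably gathered. What is missing is a named data item and its use.
- The Introduction describes true intra-articular pain as localized to the involved joint, so VAS may be joint-specific. Clicking, disc position and lateral excursion can be recorded by side. The point is firmest for MIO and protrusion.
- A reader might set a 1.8 mm shift against the planned 0.61 mm and infer bias between Levels I and II. Concealed randomization prevents systematic bias from this source. The shift lies within a 2.8 mm standard error and is ordinary sampling error.
- A reader might call the other joint a strong prognostic factor. The documents do not show that. The Introduction's statement that "MRIs in asymptomatic subjects demonstrate disc displacement in the range of 32-38" per cent concerns people without symptoms and shows no functional limit.
- Because the planned MIO measure is improvement from the preoperative value, a stable restriction may be partly absorbed. How far is unknown.

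**Conclusion.** The gap is real and its consequence is conditional. The selection rule does not say which joint is staged, and the plan makes no analytic use of the other joint. If one joint per patient is operated on, a second restricting joint can add avoidable variance to MIO and protrusion, and to VAS if it is not recorded per joint, with room for chance imbalance at 10 per arm.

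The gain from adjusting ranges from about 1% to about 20% of the interval width. The upper part of that range requires losses larger than the planned Level III SD can accommodate, unless they come on top of it. Prevalence and loss are assumptions throughout.

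The documents do not support the stronger readings that the comparison is biased, that the main Level III result is at risk, or that adjustment would rescue Level I versus II. For a loss of equal size in every arm at 30% prevalence, the Level III contrasts are detected either way. Only an extreme proportional loss would change that, and nothing in the protocol points to one. The case for acting rests on low cost and a reproducible eligibility rule.

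**What to change.** 1. In Eligibility Criteria, state that stage III refers to a named study joint, and state whether one or both joints are operated on in a patient with bilateral disease.
2. From the preoperative examination and MRI already required, record before allocation whether the other joint is symptomatic with restricted motion or locking (yes/no). Displacement on MRI alone should not trigger a yes, given its frequency in people without symptoms.
3. Tabulate this item by arm. Include it as a prespecified covariate in the models for MIO and protrusion, and for VAS if that is not recorded per joint. State whether VAS is per joint.

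The cost is one baseline item and one degree of freedom, with an interval about 2% wider if the factor proves not to be prognostic. No extra patients or visits are needed. The covariate reduces residual variance but would not restore a contrast shrunk by a proportional loss; tabulating the factor would at least help readers judge that possibility.

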Resorbable pins are Smart Nail (ConMed, Linvatec, Tampere, Finland), 1.5mm _ 16mmsize (head of pin 2.5mm in diameter and flange of 1 mm) and manufactured of polylactic acid copolymer (Self-Reinforced 96L/4D PLA). The mean degradation period was standardized between 18 and 26 months. ⁽³¹⁾

Pre-surgical evaluation

All patients will be subjected to full history taking, full clinical examination and investigations including preoperative MRI and Panoramic x-ray to assess the dental condition.

Surgical technique

- 1- All procedures will be done under general anesthesia (nasotracheal intubation).**
- 2- The triple-channel arthroscopic technique of McCain et al is used⁽³²⁾**

After the first puncture of the fossa, a systematic diagnostic arthroscopy is carried out. A second puncture is carried out aiming at the anterior recess under direct arthroscopic visualization (Level I).

3- Anterior release: (*Level II*)

Through the working cannula additional local anesthesia is injected to avoid post-operative pain and to decrease bleeding; it can also reduce the risk of masticatory muscle nerve injury. A Knife, coblation or laser probe are used to cut the anterior attachment of the disc and the neighboring part of the lateral pterygoid muscle. The incision line is located approximately 2–3 mm anterior to the anterior band of the disc and is

carried out across the whole width from medial to lateral. The depth of the anterior release is no more than 2 mm to avoid breaking large blood vessels and damaging the masticatory muscle nerve in the anteromedial synovium.

5- Retrodiscal scarification or contracture

Retrodiscal tissue is contracted using bipolar cautery, laser, or coblation. The target area of the retrodiscal contracture is generally the boggy and redundant synovium found lateral to the oblique protuberance. Contracture is visible during the procedure, but the most significant contracture occurs 2 to 3 weeks postoperatively as the scar thickens. The purpose of the contracture is to enhance the posterior positioning of the disc and hold it there. The posterior synovectomy and the scar contracture are also done to reduce volume of the joint space so the disc can sit more posteriorly.

6- Disc reduction

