After the anterior release is completed, the obturator is positioned at the anterior margin of the disc and the disc is pushed backwards. The obturator slides along the surface of the disc and arrives in the posterolateral recess. The retrodiscal tissue is pushed down inferiorly and posteriorly.

7- Disc fixation: (Level III)

A disc fixation can be accomplished in 1 of 2 ways. The first and more traditional way is the suture discopexy. A second way is by rigid fixation with either resorbable or titanium screws. Regardless of the methodology of fixation, the disc is held in reduction during the course of the fixation. The target area of fixation is the posterior lateral corner of the disc-condyle assembly, the area of the lateral pole where the disc attaches to the condyle.

Postoperative management

Antibiotics and nonsteroidal anti-inflammatory drugs are routinely prescribed for 5 days. The softness of the postoperative diet should be decreased slowly. Exercises to improve mouth opening are explained to the patient and start 1 week after operation.

In patients with significant postoperative occlusal changes, a splint is recommended. It is designed to raise the bite and prevent contact between upper and lower incisors and canines. Due to the resulting distalization of the bite force, joint loading is reduced, which contributes to the joint's rehabilitation. The appliance should be left in place around the clock during the first ten postoperative days, then used at night for four additional weeks.⁽³⁴⁾

Follow up

- Pain assessment using VAS (Visual Analogue Scale) ⁽²⁵⁾

- Clicking (improvement or persistence).
- Range of motion ⁽³³⁾ including: maximal interincisal opening, lateral excursion movement and Protrusive movement
- Post-operative MRI at 6 months for detection of disc position.
- All patients will be followed up at 1, 3, 6 months.

ETHICAL CONSIDERATIONS

Research Ethics Committee approval

The research protocol will be approved by the Research Ethics Committee of Alexandria University Faculty of Dentistry (IRB No. 001056 – IORG 0008839) prior to any research-related activities

All research activities involving human subjects will abide with the Declaration of Helsinki ⁽³⁴⁾ and other ethical guidelines adopted by the Research Ethics Committee of Alexandria University Faculty of Dentistry.

The benefits to the participant and/or the community

1. Treatment of patients with internal derangement with minimally invasive surgery (TMJ arthroscopy).

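### No complication outcome is collected by arm, although the protocol itself names vessel, nerve and occlusal hazards and the results are meant to guide the choice of arthroscopy level

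*Combined protocol and SAP*

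**What the plan says.** **Outcomes.** In Aim of the study, the primary aims are VAS pain, clicking, mouth opening, lateral excursion and protrusion. The secondary aims are operative time and disc position on postoperative MRI. Follow up lists the same clinical items at 1, 3 and 6 months, with MRI at 6 months. Data management & statistical analysis is one sentence naming ANOVA.

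**Hazards.** Surgical technique, step 3 (anterior release, labelled Level II) limits the depth of the cut to "avoid breaking large blood vessels and damaging the masticatory muscle nerve in the anteromedial synovium". The same step justifies local anaesthetic partly by less bleeding and a lower risk of nerve injury. Postoperative management, which applies to all groups, adds: "In patients with significant postoperative occlusal changes, a splint is recommended".

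**Risk list.** Under Ethical considerations, the risks to the participant are two: "The need for long-term follow-up postoperative" and "The exposure to radiation in MRI which is needed for follow-up at 6 months".

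**Purpose.** The Abstract and the end of the Introduction say that the comparison is meant to yield patient selection criteria, treatment options and guidelines for others to use.

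**The concern.** The Introduction describes Level I as the most basic and Level III as more advanced. Choosing between them means weighing any gain in mouth opening or pain against what the extra steps may cost the patient. The protocol is alert to such costs when it describes the operation, but it schedules no record of them.

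The gap matters most if the levels prove similar on the primary outcomes. That is the stated null hypothesis, and the Introduction cites a review in which disc repositioning succeeded about as often as lysis and lavage. Complications might then weigh heavily in the choice, and the trial would have no planned data on them. Analysis cannot repair this, because an event not recorded systematically at the time cannot be recovered reliably later.

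**Working it through.** **The plan's own figure.** The only stated design figure is the sample size, and this point does not rest on it. The inputs, from Sample size calculation, are: "The size was estimated based on 5% alpha error and 80% study power"; mean (SD) gains of "6.09 (7.05) mm for Level I arthroscopy", "6.7 (5.25) mm for Level II arthroscopy" and "18.5 (2.1) mm for Level III arthroscopy"; and a pooled SD of 4.8 mm.

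- The 4.8 is the plain average of the SDs: (7.05 + 5.25 + 2.1)/3 = 4.8.
- Grand mean = (6.09 + 6.7 + 18.5)/3 = 10.43. The deviations are −4.34, −3.73 and 8.07, and their root mean square is 5.71. So f = 5.71/4.8 = 1.19.
- Power of the one-way F test at alpha 0.05 is 68.7% with 3 per group, 88.0% with 4 and 99.97% with 9. The minimum is therefore 4 per group, and the stated 9 is not reproduced.

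That mismatch is a separate matter. Only the resulting group sizes, 10 enrolled and 9 allowing for loss, are used below.

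**Named hazards against planned records.**

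- Bleeding or vessel injury (Surgical technique, step 3): no entry in the aims, Follow up or analysis.
- Masticatory nerve injury (same step): no entry.
- Significant occlusal change (Postoperative management): a splint is foreseen, but neither the change nor the splint is recorded as an outcome.

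Step 3 is labelled Level II. Group III is described as operative arthroscopy plus repositioning and fixation, so the release applies to two of the three groups, 20 of 30 participants. Occlusal change is linked to no level.

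**What a recorded outcome could show with these numbers.** The documents give no complication rates, so the rates below are assumptions for illustration.

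- *Upper limit after no events.* Two-sided 95%: 1 − 0.025^(1/10) = 30.8%, and with 9 evaluable 1 − 0.025^(1/9) = 33.6%. One-sided 95% with 10: 1 − 0.05^(1/10) = 25.9%.
- *Chance of at least one event in a group of 10*, 1 − (1 − p)^10: 9.6% at p = 1%, 40.1% at 5%, 65.1% at 10% and 89.3% at 20%.
- *Two groups compared by Fisher's exact test, two-sided.* 0/10 v 4/10: p = 2 × 210/4845 = 0.087. 0/10 v 5/10: p = 2 × 252/15504 = 0.033.
- *Power of that test with 10 per group.* 2.0% for 5% v 20%, and 9.3% for 5% v 30%. For 80% power these contrasts need about 76 and 36 per group (normal approximation).

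The outcome is therefore worth recording and describing, but not testing.

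**The case against.** Several stronger readings are tempting, and the documents do not support them.

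- *A reader might infer that the trial measures benefit only.* Operative time is a measure of burden. Pain and range of motion can worsen, and the 6-month MRI may partly show loss of disc position. These are real but indirect signals. None identifies bleeding, a nerve deficit, occlusal change or a second operation.
- *A reader might infer that all the named harms rise with the level.* Only the bleeding, vessel and nerve hazards are tied to a level, and there as dangers that the technique is designed to avoid. Occlusal change is not tied to any level. No rates are given, so a difference in harm between levels is plausible but not shown.
- *A reader might infer that complications would be lost altogether.* Clinical records are not ruled out, and giving a splint requires someone to notice the occlusal change. What is missing is prespecified, systematic collection by arm.
- *A reader might infer from the risk list that participants are not told of surgical hazards.* Consent pages are not part of the available text, so this cannot be judged. What can be said is that the risk list and the technique section do not agree.

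The best remaining objection is that 10 per group is too few to learn much about harm. That is correct for ranking the levels. It is not a reason to leave the data uncollected: a single serious event is informative, and small trials can be combined on harm only if each reports it.

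**Conclusion.** The concern holds in a limited form. The aims, follow-up list and analysis sentence contain no complication item, although the protocol names vessel and nerve hazards at a step used in two of its three arms and foresees occlusal change after surgery. Followed as written, the trial would support guidelines on three levels of surgery without systematic harm data by arm.

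The size of any harm difference cannot be computed, because the documents give no rates. Nor would adding the outcome make the trial able to rank the levels on harm: an arm with no events would remain compatible with a true rate of up to 30.8% (10 evaluable) or 33.6% (9 evaluable), and even 0/10 v 4/10 would not reach p < 0.05. These limits assume independent observations, one per participant.

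This is a cheap improvement that should be made. It does not invalidate the efficacy comparison.

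**What to change.** - Add to the secondary aims, and to Follow up, intraoperative and postoperative complications by arm. Include at least bleeding or vessel injury, nerve deficit, occlusal change for which a splint is given, and reoperation. Write a definition for each item before use; the protocol's word for occlusal change, significant, is not defined.
- Record them at surgery and at the existing 1-, 3- and 6-month visits, with the same questions and examination in every group.
- In the analysis section, state that complications are reported as counts per arm with exact 95% confidence intervals and no significance test.
- Reconcile the risk list under Ethical considerations with the hazards named in Surgical technique and Postoperative management.

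The cost is a few items on the operative and visit forms and one descriptive table, with no extra patients or visits. The downside is imprecision, which the report should state so that an empty cell is not read as evidence of safety.
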